2.0 OBJECTIVES

This is a phase II study designed to prospectively evaluate the efficacy and safety of DE CK-SBRT for unfavorable risk prostate cancer in a community setting.

Hypothesis

1. Dose Escalated Stereotactic Body Radiation Therapy is adequate for biochemical control of Unfavorable Intermediate and High Risk Prostate Cancer.

Primary Objective

1. To assess efficacy endpoints: Biochemical disease-free survival (bDFS) assessed using the Phoenix definition (55), duration of local control, distant failure and site of distant failure, disease-free survival, disease-specific survival and overall survival.

Secondary Objectives

1. To estimate the proportion of patients who develop late (> six months) grade 3-5 gastrointestinal and genitourinary toxicity observed following SBRT for prostate cancer.
2. To evaluate Quality of life (QOL) using standardized instruments.

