Patients will receive five SBRT treatments of 8 Gy each. The total dose will be 40 Gy. The five treatments will be completed in 7-10. A minimum of 20 hours should elapse between treatments. The total duration of treatments should take no longer than 10 days.

Target Volumes:

Gross Tumor Volume (GTV): The GTV shall include the prostate and any gross extension. 2cm of the SV will be contoured separately. Malignant Nodules identified on MRI will be contoured separately.

Planning Tumor Volume (PTV): The prescription dose (8 Gy) shall be delivered to the PTV. The PTV shall equal the CTV expanded 3 mm in all other directions. Any malignant nodules identified on endorectal/Multi parametric MRI will be prescribed an integrated boost of 10Gy per fraction while respecting all dose constraints. (9 Gy per fraction will be considered an acceptable variation if dose constraints cannot be met.) The PTV-SV will receive 7.25 Gy per fraction.

SBRT Dose Specifications:

PTV: The prescription dose of 40 Gy shall be the dose to the PTV: Per protocol, the volume of the PTV receiving 40 Gy (V40 Gy) shall be at least 95%. The PTV-SV will be treated to 36.25 Gy and the PTV-SV receiving 36.25 Gy shall be at least 95%.

Rectum: Per protocol, the volume of the rectum receiving 36 Gy (V36 Gy) shall be < 1cc. The rectal dose-volume histogram (DVH) constraints are < 50% rectal volume receiving 50% of the prescribed dose, < 20% receiving 80% of the dose, < 10% receiving 90% of the dose, and < 5% receiving 100% of the dose

Bladder: Per protocol, the volume of the bladder receiving 40Gy (V40 Gy) shall be < 5 cc. Although not required, the bladder dose-volume histogram (DVH) goals are < 40% bladder volume receiving 50% of the prescribed dose, < 10% receiving 100% of the dose.

Bladder Neck: Per protocol, the maximum dose (0.03 cc) to the bladder neck should be \leq 40 Gy.

Sigmoid colon and other bowel: Per protocol, the volume of the sigmoid colon and other bowel receiving 36 Gy (V36Gy) shall be < 1cc.

Prostatic urethra: Per protocol, the maximum dose (0.03 cc) to the prostatic urethra should be < 43 Gy.

Membranous urethra: Per protocol, the maximum dose (0.03 cc) to the membranous urethra should be < 43 Gy.

Penile bulb: Per protocol, the volume of the penile bulb receiving 35 Gy (V35Gy) shall be < 50%. Minor variations: V35Gy \geq 50%, but < 75%. Major variations: V35Gy > 50%.

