5.0 ANDROGEN SUPPRESSION

Androgen suppression (ADT) consists of LHRH agonist for a total of 6 months for unfavorable intermediate risk patients and 18 months for high and very high-risk patients. The choice of LHRH agonist is at the discretion of the treating physician. ADT should proceed initiation of SBRT however there is no minimum interval of ADT prior to initiation of SBRT which is patient/physician defined but should not exceed 6 months.

Risks of Androgen Suppression

ADT has several reported adverse and serious adverse reactions that have been reported in patients with advance prostate cancer who received Orgovyx (ADT oral use tablets). The most common adverse reactions hot flush, musculoskeletal pain (including arthralgia, back pain, pain in extremity, musculoskeletal pain, myalgia, bone pain, neck pain, arthritis, musculoskeletal stiffness, non-cardiac chest pain, musculoskeletal chest pain, spinal pain, and musculoskeletal discomfort), fatigue, diarrhea, and constipation.

Serious adverse reactions occurred in 12% of patients who received ADT. Serious adverse reactions in \geq 0.5% of patients included myocardial infarction (0.8%), acute kidney injury (0.6%), arrhythmia (0.6%), hemorrhage (0.6%), and urinary tract infection (0.5%). Fatal adverse reactions occurred in 0.8% of patients receiving ADT including metastatic lung cancer (0.3%), myocardial infarction (0.3%), and acute kidney injury (0.2%). Fatal and non-fatal myocardial infarction and stroke were reported in 2.7% of patients receiving Orgovyx.

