Quality-Adjusted Life Years (QALY): **EuroQol EQ-5D-5L** is a validated instrument which provides a single index value for a patient’s overall health status (otherwise known as “utility”). It is widely used in cancer clinical trials (56, 57). Five of the items are scored on a 3-point Likert scale (mobility, ability for self-care, ability to perform usual activities, pain/discomfort, anxiety/depression), and one item assesses a patient’s overall health state on a visual analog scale ranging from 0 (worse imaginable state) to 100 (best imaginable).

8. STATISTICAL CONSIDERATIONS:

Endpoints:

Primary Endpoint

1. **Toxicity** will be assessed using the NCI Common Toxicity Criteria version 4.0.

Secondary Endpoints

1. **Biochemical disease-free survival (bDFS)** will be defined as the time in months from completion of SBRT to biochemical failure. Patients who are free from biochemical failure on the date of closing follow-up will be censored on that date. The Phoenix definition will be used to assess biochemical failure as described in Section 10.
2. **Duration of local control** will be defined as the time in months from SBRT completion to local failure.
3. **Distant failure (includes regional failure)** will be defined as the time in months from SBRT completion to distant failure.
4. **Disease-free survival** will be defined as the time in months from the date that the patient is determined to be free of disease to the date of known disease recurrence for any measure of disease. Patients who are alive and free from disease recurrence on the date of closing follow-up will be censored on that date.
5. **Disease-specific survival** will be defined as the time in months from completion of SBRT to death due to prostate cancer, other causes with active malignancy, or complications from treatment. Patients who are alive or dead with disease relapse but with inactive disease on the date of closing will be censored on that date.
6. **Overall survival** will be defined as the time in months from SBRT completion until death. Patients who are alive on the date of closing will be censored on that date.
7. **Quality of life**

Study Design:

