The target sample size is 100 patients for this Phase II study. Allowing for a 15% ineligibility rate, the total sample size is 115 patients. Accrual is anticipated to be completed within 5 years of institutional IRB approval. This Phase II trial will provide information to guide future Phase III studies. Sample size determination is based on the late toxicity endpoint. A single-stage Fleming design will be used to test the null hypothesis that the late unacceptable radiation toxicity probability at 2 years p is < 0.05 versus the alternative hypothesis that toxicity probability at 2 years is > 0.15 . Unacceptable toxicity will be defined as grade 3 or higher toxicity. If 10 or fewer patients experience late radiation toxicities at 2 years, the null hypothesis will not be rejected and then the regimen will be considered for a phase III study. If at least 10 patients experience late radiation toxicities at 2 years, the null hypothesis will be rejected. This design has a power of 89% and a type I error rate of 0.10.

Analysis Plan

1. Number and percentage of subjects for each toxicity will be summarized overall by body system and by onset time (acute: ≤ 90 days of treatment start and late: >90 days of treatment start). The tabulation will also be separated by toxicities of Grade 3 and above.
Future studies incorporating DE-SBRT would be worthwhile if the rate of grade 3 GU/GI toxicity was $\leq 10\%$.
2. Biochemical disease-free survival, disease-free survival, disease-specific and overall survival curves will be calculated and presented by the methods of Kaplan and Meier.
3. The proportion of patients with local and distant failure will be reported with a 95% binomial confidence interval.
4. General health related and disease specific quality of life measurements will be summarized over time. Graphical displays will be created for each patient's trajectory over time and also summarized using the average for all patients.

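### Scheduled ADT outlasts SBRT by about 0-6 months in unfavorable intermediate risk and 12-18 months in high and very high risk, so the all-patient QOL average and an unsplit early bDFS curve cannot be attributed to DE-SBRT alone

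*Protocol*

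**What the plan says.** Section 5.0 sets ADT "for a total of 6 months for unfavorable intermediate risk patients and 18 months for high and very high-risk patients". On timing before radiation it says that "there is no minimum interval of ADT prior to initiation of SBRT which is patient/physician defined but should not exceed 6 months". Section 4.0 limits the length of the SBRT course: "The total duration of treatments should take no longer than 10 days".

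Section 8, Secondary Endpoints item 1, says that bDFS "will be defined as the time in months from completion of SBRT to biochemical failure". Analysis Plan item 2 says: "Biochemical disease-free survival, disease-free survival, disease-specific and overall survival curves will be calculated and presented by the methods of Kaplan and Meier". It names no strata. Item 4 plans individual QOL trajectories, "also summarized using the average for all patients".

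The hypothesis in Section 2.0 is that DE-SBRT is "adequate for biochemical control of Unfavorable Intermediate and High Risk Prostate Cancer". Section 1.0 defines three risk groups, and Section 8 does not use them. Section 7.0 places EPIC-26 at 6 months, 12 months and yearly after that, and the table in Section 6.0 gives EQ-5D-5L the same visits. Section 7.0 also notes that EPIC covers hormonal symptoms.

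**The concern.** Risk group fixes the length of ADT, so prognosis and PSA suppression are tied together. Every clock in the trial starts at SBRT, yet the hormonal exposure that follows differs by 12 months between the groups at equal lead-in. This affects two outputs.

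- **QOL.** A single mean at 6 or 12 months combines men on ADT with men off it. Part of any change in hormonal or sexual scores may come from ADT. Part of any later recovery may come from ADT ending, and not from recovery after radiation.
- **bDFS.** Time under scheduled ADT counts as time free of biochemical failure, and there is more of it in the groups with the worse prognosis. The level of one unsplit curve then depends on a case mix that the protocol does not fix.

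The only stated hypothesis is about biochemical control in named risk groups. Section 2.0 lists bDFS under the primary objective, although Section 8 calls it secondary. A pooled early figure cannot answer that hypothesis for either group.

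**Working it through.** The protocol gives no sample size, power or target rate for bDFS or QOL, so there is no stated figure to reproduce.

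**Step 1: ADT left after SBRT.** Inputs: total ADT 6 or 18 months and lead-in 0-6 months (Section 5.0); SBRT course up to 10 days, about 0.33 month (Section 4.0).

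Remaining after SBRT start = total − lead-in.

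| Group | Lead-in 6 months | Lead-in 0 | From SBRT completion (10-day course) |
|---|---|---|---|
| Unfavorable intermediate | 6 − 6 = 0 | 6 − 0 = 6 | about 0 to 5.7 |
| High and very high | 18 − 6 = 12 | 18 − 0 = 18 | about 11.7 to 17.7 |

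At equal lead-in the gap is 18 − 6 = 12 months.

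**Step 2: who is on ADT at each visit.**
- Month 6: essentially no intermediate-risk man, and every high or very high risk man.
- Month 12: nearly every high or very high risk man. Those with the full 6-month lead-in have just stopped (11.7 < 12).
- Month 18 onward: scheduled ADT has ended in all (17.7 < 18).

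The risk mix is not given. Assuming a high/very high share h of 25%, 50% or 75% and lead-ins spread evenly over 0-6 months, about 25%, 50% or 75% of the cohort is on ADT at both month 6 and month 12.

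**Step 3: the pooled QOL mean.** Let m be the intermediate-risk mean at a visit and d the difference of the high/very high mean from it. The pooled mean is (1 − h)·m + h·(m + d) = m + h·d. Moving h from 25% to 75% shifts the pooled mean by 0.5·d with no change in either group. The documents give no value for d.

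**Step 4: bDFS, illustration only.** Assume no failures on ADT and a constant hazard λ afterwards. Freedom from failure at month v is the average over lead-ins of exp(−λ × months since ADT ended). With lead-ins spread evenly over 0-6 months (mean 3), the mean time since ADT ended at month 24 is 24 − 3 = 21 months (intermediate) or 24 − 15 = 9 months (high/very high). At month 60 it is 57 or 45 months. The 10-day course is ignored here.

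*Equal hazards*, with λ = −ln(S)/60 and S the assumed 60-month freedom from failure without any delay:

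| S | Month | Intermediate | High/very high | Difference (points) |
|---|---|---|---|---|
| 80% | 24 | 92.5% | 96.7% | 4.2 |
| 90% | 24 | 96.4% | 98.4% | 2.0 |
| 80% | 60 | 80.9% | 84.6% | 3.7 |
| 90% | 60 | 90.5% | 92.4% | 1.9 |

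As h goes from 25% to 75%, the pooled 24-month value moves from 93.5% to 95.7% (S = 80%) or from 96.9% to 97.9% (S = 90%).

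*Unequal hazards*, with S = 95% in intermediate and 80% in high/very high risk: at month 24 the groups stand at 98.2% and 96.7%, and at month 60 at 95.2% and 84.6%. The order reverses. The pooled 60-month value falls from 92.6% (h = 25%) to 87.3% (h = 75%), so an unsplit curve then depends mainly on case mix.

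**The case against.** The strongest reply is that a split by risk group is ordinary SAP content, and the SAP is not shown. The protocol defines the groups, and Analysis Plan item 2 neither pools nor excludes strata. This stands for bDFS: pooling there is inferred because no split is named. It does not stand for QOL, where the all-patient average is explicit. Individual trajectories are planned beside it, but they do not separate the groups.

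Three further points stand.
- Timing bDFS from SBRT completion is not itself an error. It matches the origin used for local control, distant failure, disease-specific survival and overall survival.
- The consequence is limited. Sample size and the phase III decision rest on late toxicity, bDFS has no target rate or test, and follow-up runs to 5 years, well beyond scheduled ADT.
- Splitting by group does not isolate SBRT, because every man in each group is scheduled for both treatments.

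A reader might infer that early results show ADT and risk mix and nothing of DE-SBRT. The documents do not support that. This is a single-arm trial of SBRT with ADT, so early results contain the effects of both and cannot be divided. A reader might also infer that the high-risk group is bound to look several points better from timing alone. That needs equal hazards and no failures on ADT, which the protocol does not state. With a higher hazard in that group the gap shrinks or reverses, as the last illustration shows.

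**Conclusion.** The point holds in a limited form, as a worthwhile improvement to the reporting. ADT exposure after SBRT differs by 12 months between risk groups at equal lead-in. The 6- and 12-month QOL averages therefore mix men on and off ADT, and early bDFS shown without a split combines SBRT, ADT and risk mix. Neither can be credited to DE-SBRT alone.

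The exposure figures follow from the protocol to within 10 days. They are scheduled durations, so actual use may differ. The share of the cohort on ADT at the early visits rests on an assumed risk mix. The bDFS shifts of about 1 to 4 points under equal hazards are illustrations, and even their direction between groups depends on the assumed hazards. The problem is greatest early, but an offset from delayed failures can persist: 1.9 to 3.7 points at month 60 in the equal-hazard cases. The late-toxicity decision rule is not affected.

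**What to change.** In Analysis Plan items 2 and 4, present bDFS curves and EPIC-26 and EQ-5D-5L means separately for two groups: unfavorable intermediate (6-month ADT) and high plus very high risk (18-month ADT). Keep the pooled summary as descriptive. State that the results are those of SBRT plus ADT. Base each group's statement on biochemical control on the 5-year estimate, and note that a timing offset may remain.

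A bDFS clock started at the end of ADT is not advised. It has no defined value for men who fail while on ADT, and in an intermediate-risk man with a full 6-month lead-in it would start before SBRT is complete. If a supplementary analysis is wanted, use a landmark after scheduled ADT has ended in all, for example 18 months after SBRT completion, restricted to men then free of failure and still in follow-up.

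The change is a matter of analysis wording and uses groups the protocol already defines. Treatment, visits and sample size stay as they are. The cost is wider intervals within each group.

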6.0 PATIENT ASSESSMENTS

| Assessment | Pre-entry | | | | Follow-up interval: months post therapy | | | | |
|----------------------------|-----------|---|---|---|---|----|----|-------|---|
| | | 1 | 3 | 6 | 12 | 18 | 24 | 36-60 | |
| History (SHIM, AUA) | X | | X | X | X | X | X | | X |
| Physical exam (DRE) | X | | | X | X | X | X | | X |
| ECOG Performance Scale | X | | | X | X | X | X | | X |
| Prostate Biopsy | X | | | | | | | | |
| PSA | X | | | X | X | X | X | | X |
| Prostate volume assessment | X | | | | | | | | |
| Bone scan | X | | | | | | | | |
| Pelvic imaging | X | | | | | | | | |
| Toxicity evaluation (AUA) | X | | X | X | X | X | X | | X |
| EPIC-26 Questionnaire | X | | | | X | X | | X | X |
| EuroQol EQ-5D-5L | X | | | | X | X | | X | X |

Assessment schedule: Quality of life measurements will take place per the table, then annually through 5 years post-treatment.

7.0 CLINICAL ENDPOINTS:

Patients will have toxicity evaluation weekly during treatment. At 1 month following treatment, patients will be assessed for acute toxicity. At 6, 12, 18, and 24 month intervals (and every year thereafter, through year 5- 10, if investigators opt to continue past year 5), patients will be seen and evaluated, including a history, physical exam, performance status, PSA, toxicity evaluation. In addition, at 6 months, 12 months and annually thereafter, EPIC-26 will be administered. Examination and studies may be done at outside facility. Prostate biopsy, bone scan (PSMA PET/CT may be substituted for bone scan) and pelvic MRI will be performed at time of biochemical or clinical failure.

Criteria for toxicity:

Acute side effects (<=90 days of treatment start) and late side effects (> 90 days of treatment start) will be assessed using the NCI Common Toxicity Criteria version 4.0 (see appendix V).

Criteria for disease control:

1. Biochemical disease free survival (bDFS):
 - a. Phoenix definition (55): failure occurs when the PSA is ≥ 2 ng/ml more than the lowest PSA measurement before the current one, with no backdating. Administration of salvage therapy will be considered failure.

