2. Duration of local control: clinical evidence of local progression or recurrence. Clinical failure includes a palpable abnormality that has increased in size, failure of regression of a palpable abnormality by 2 years after treatment, or redevelopment of a prostate abnormality after complete response. Patients with a prostate abnormality compatible with local recurrence, or a PSA failure shall undergo a prostate biopsy. Histologic criteria for local failure is a positive prostate biopsy more than 2 years after treatment. Patients

with a normal exam and no evidence of PSA failure shall be considered controlled locally. Patients with clinical failure and no biopsy are considered local failures. If a patient is locally controlled at the time of orchiectomy or androgen ablation, he is censored and considered “not evaluable” for further local control.

3. Distant failure (includes regional failure): documented if clinical, bone scan, CT or other imaging study shows metastatic disease. Biochemical failure with a negative prostate biopsy shall be considered distant only failure. Biopsy of metastatic site required if radiographic or clinical findings are equivocal. Type of metastatic failure (distant and/or regional) shall be recorded if known. Prostate biopsy recommended at this time.
4. Disease-free survival: for any measure of disease, including PE, PSA, bone scan, CT/MRI and biopsy, or death.
5. Disease-specific survival: for any of the following: Death due to prostate cancer. Death due to other causes, with active malignancy (defined by clinical or biochemical evidence of progression). If a patient suffered a previous relapse, but has inactive disease, this is not considered a disease-specific death. Death due to complications of treatment.
6. Overall survival: for death from any cause.

Quality of Life/Health Outcomes instruments (See Appendix VI):

1. Disease-specific quality of life: The **Expanded Prostate Cancer Index Composite (EPIC)-26** is a validated comprehensive instrument developed to assess patient function and bother after prostate cancer treatment. It was developed by an expert panel of urological oncologists, radiation oncologists, survey researchers, and prostate cancer nurses, to address symptoms related to radical prostatectomy, radiotherapy, and hormonal symptoms.

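### Section 8 starts disease-free survival at a disease-free date that the protocol never defines, so patients whose palpable disease never regresses may be left off the curve; its event clause also omits death, which Section 7 counts

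*Protocol*

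**What the plan says.** DFS is described in two places in the Protocol.

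- **Section 7.0, Criteria for disease control, item 4** gives the event: "for any measure of disease, including PE, PSA, bone scan, CT/MRI and biopsy, or death". It gives no time origin.
- **Section 8, Secondary Endpoints, item 4** gives the origin and the event. DFS "will be defined as the time in months from the date that the patient is determined to be free of disease to the date" of the event, and the event clause reads "to the date of known disease recurrence for any measure of disease". The censoring sentence is: "Patients who are alive and free from disease recurrence on the date of closing follow-up will be censored on that date".

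The other five time-to-event endpoints in Section 8 (biochemical DFS, local control, distant failure, disease-specific survival and overall survival) all run from completion of SBRT.

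Two parts of Section 7 bear on the origin. Patients are examined and have PSA measured "At 6, 12, 18, and 24 month intervals" and yearly after that. Under local control (item 2), patients "with a normal exam and no evidence of PSA failure shall be considered controlled locally", and clinical failure includes "failure of regression of a palpable abnormality by 2 years after treatment".

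The Section 8 Analysis Plan calls for a Kaplan-Meier DFS curve (item 2) and for the proportions with local and distant failure (item 3). Section 2.0 names "disease-free survival, disease-specific survival and overall survival" under the primary objective, whereas Section 8 lists DFS as secondary.

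**The concern.** A Kaplan-Meier curve needs one start date and one status for every patient. The Section 8 definition falls short on both counts.

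The start date is the main problem. The clock begins at a determination that the protocol does not define, and some patients may never receive it. Those patients are not a random subset. A man whose palpable abnormality never regresses is a treatment failure by the protocol's own criterion, and leaving him out makes the curve look better.

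The status problem is smaller. Read alone, the Section 8 clause gives a death without recurrence no status: it is not a known recurrence, and the patient is not alive to be censored.

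At stake is whether the published DFS curve is reproducible and includes all treated patients. In a single-arm trial meant to guide later phase III work, that curve will be read as a result in its own right.

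**Working it through.** The protocol states no figure that rests on DFS, so there is none to reproduce. The check is a comparison of the text, followed by one illustration.

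**Step 1: is the start date defined anywhere?** The nearest text is the local-control rule in Section 7 item 2 (normal examination, no PSA failure). That rule classifies local control only; it is not called disease-free status and it sets no date. The same item mentions complete response without defining it. After treatment, biopsy, bone scan and pelvic MRI are called for only at biochemical or clinical failure. The scheduled information is therefore examination and PSA, and no rule turns these into a DFS start date.

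**Step 2: follow one patient through both sections.** His palpable abnormality persists through the 2-year visit.

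| Question | Section 7 | Section 8 item 4 |
|---|---|---|
| Has he failed? | Yes, clinical failure by 2 years | Only if persistent disease counts as recurrence |
| When does his DFS clock start? | Not stated | When determined free of disease, which may never happen |
| Is he on the DFS curve? | He has an event by physical examination | Possibly not |

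He would still be counted in the local-failure proportion.

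**Step 3: follow a patient who dies without recurrence.** Section 7 makes the death an event. The Section 8 event clause does not name it, but the censoring sentence excludes it by requiring the patient to be alive. The disease-specific survival item just below expressly censors some patients who have died; the DFS item does not. Read together, the two sections point to death as an event.

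**Step 4: illustrate the size of the dropped-patient effect.** All rates here are assumptions, because the protocol gives none.

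- Recurrence by 5 years of 15%: h = −ln(0.85)/5 = 0.0325 a year.
- Other-cause death: d = 0.01 a year.
- DFS at 5 years for patients who have a start date, death counted as an event, clock from SBRT completion: S = exp(−5(h + d)) = 0.85 × exp(−0.05) = 0.8085.
- A fraction q never regresses, and all of these fail by 2 years. With them included, DFS = (1 − q)S; with them dropped, DFS = S. The difference is qS.

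| q | DFS, included | DFS, dropped | Rise (points) |
|---|---|---|---|
| 1% | 0.99 × 0.8085 = 80.0% | 80.9% | 0.8 |
| 3% | 0.97 × 0.8085 = 78.4% | 80.9% | 2.4 |
| 5% | 0.95 × 0.8085 = 76.8% | 80.9% | 4.0 |

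Since S is at most 1, the rise can never exceed q itself.

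**The case against.** **The death wording is largely resolved by the document.** This stands. Section 7 names death, and the Section 8 censoring sentence is confined to the living. A reader might infer that the protocol holds two rival DFS rules and that the curve could move a long way according to which is used. Censoring deaths without recurrence, for example, would give 85% instead of 80.9% under the rates above, a gap of 4.1 points. The documents do not support that inference. Neither section states such censoring, and it is contrary to Section 7 and to the condition of being alive in Section 8. Under the reading that the text supports, the gap is zero. What remains is an incomplete clause to be aligned.

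**A late start date need not bias DFS in a known direction.** This also stands. A reader might infer that starting the clock at a visit 6 to 24 months after SBRT must flatter the result. With a constant recurrence hazard, a recurrence-only 5-year figure of 85.0% does not change. With a falling hazard (Weibull shape 0.7) it becomes 86.8% to 88.7%; with a rising one (shape 1.5), 83.3% to 79.6%. The sign depends on a hazard shape that the documents do not give. The comparison also needs 5.5 to 7 years of follow-up from SBRT, and follow-up past year 5 is optional.

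**Section 7 supplies the event for never-regressing patients, and an SAP could fix the date.** This stands in part. Section 7 does make them failures, and the choice of visit for a status date is often left to an SAP. But the protocol has itself fixed an origin that some treated patients may never reach. That is a flaw in the definition rather than missing detail.

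**DFS carries little weight in the design.** This stands. It is listed as secondary in Section 8 and has no hypothesis or threshold. Its place under the primary objective in Section 2.0 reflects a separate mismatch between those sections and adds nothing to this point.

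**Conclusion.** The point holds for the time origin. DFS alone among the six time-to-event endpoints starts at a determination that is neither defined nor dated, and patients whose palpable disease never regresses may be missing from the Kaplan-Meier curve although Section 7 counts them as failures. The omission of death from the Section 8 event clause is a secondary point of alignment, because the rest of the text indicates that death is an event.

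The size cannot be taken from the documents. Under the assumed rates, dropping 1% to 5% of patients raises 5-year DFS by 0.8 to 4.0 points; the true fraction is unknown and could be lower. The sample size, the late-toxicity test and the decision rule do not depend on DFS and are unaffected. The wording should be corrected before DFS is analysed, but the point does not threaten the trial's main conclusion.

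**What to change.** Replace the definition in Section 8, Secondary Endpoints item 4, with wording such as:

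*DFS is measured in months from SBRT completion to the first of disease recurrence or failure by any measure of disease, or death from any cause.*

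In the censoring sentence that follows it, insert *or failure* after *recurrence*. Without that insertion, a living patient whose disease never regressed would be both an event and censored.

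The event then agrees with Section 7, and the origin agrees with the other Section 8 endpoints; Section 7 itself gives no origin to match.

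The cost is a small wording change in one item. The SBRT completion date and the date of death are already needed for overall survival, so no new data are required. The drawback is that reported DFS may be slightly less favourable than under a reading that leaves out patients never declared free of disease.

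### The total of 115 covers about 13% ineligibility, not the stated 15%: it yields about 98 eligible patients rather than 100, with a small effect on power

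*Protocol*

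**What the plan says.** The relevant text is in Protocol section 8, Study Design. The target is given first: "The target sample size is 100 patients for this Phase II study". The enrolment total follows directly: "Allowing for a 15% ineligibility rate, the total sample size is 115 patients". The endpoint behind these numbers is then named: "Sample size determination is based on the late toxicity endpoint".

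The test compares a null under which "the late unacceptable radiation toxicity probability at 2 years p is < 0.05" with "the alternative hypothesis that toxicity probability at 2 years is > 0.15". The decision is a fixed count. One sentence reads "If 10 or fewer patients experience late radiation toxicities at 2 years, the null hypothesis will not be rejected"; another reads "If at least 10 patients experience late radiation toxicities at 2 years, the null hypothesis will be rejected". The claimed performance is "This design has a power of 89% and a type I error rate of 0.10".

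Nowhere does the protocol give a replacement rule for ineligible patients, a rule to keep enrolling until 100 are eligible, or a cut-off that changes with the number eligible.

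**The concern.** The three figures 100, 15% and 115 are meant to fit together, and they do not. To allow for a loss that is a fraction of those enrolled, the target is divided by one minus that fraction. The protocol's total instead comes from multiplying the target by one plus the fraction, which is always too small.

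What is at stake is the denominator of the primary toxicity test. The decision is an absolute number of events, so with fewer eligible patients the same count is a little easier to stay under. A regimen with 15% late toxicity is then flagged slightly less often. The direction is unfavourable on a safety endpoint, so the size needs checking.

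**Working it through.** **Inputs, all from Protocol section 8, Study Design.** Target 100; ineligibility 15%; total 115; null rate 0.05; alternative rate 0.15; cut-off at 10 events, stated in two ways; power 89%; type I error 0.10.

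**1. Reproduce the stated total.** 100 x (1 + 0.15) = 115. This matches exactly, so the total was obtained by multiplication.

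**2. What 115 delivers at 15%.** 115 x (1 - 0.15) = 97.75 expected eligible.

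**3. What 100 eligible requires.** 100 / (1 - 0.15) = 117.6, rounded up to 118. Check: 118 x 0.85 = 100.3. The difference is 3 patients, and 3/115 = 2.6%.

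**4. What rate 115 does cover.** (115 - 100)/115 = 13.0%.

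**5. Chance of reaching 100.** Let the number eligible be binomial with probability 0.85.
- 115 enrolled: P(eligible >= 100) = 0.333, so P(fewer than 100) = 0.667.
- 118 enrolled: P(eligible >= 100) = 0.593, so P(fewer than 100) = 0.407.

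**6. Effect on power.** Power is the exact binomial probability P(X >= r) at p = 0.15, where X is the number of patients with late toxicity and r is the smallest count that rejects the null. The two decision sentences imply different values of r, so both are shown. The averaged rows weight the power at each eligible count by its binomial probability.

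| Eligible patients | Reject at 11 or more (advance at 10 or fewer) | Reject at 10 or more |
|---|---|---|
| 100 | 0.901 | 0.945 |
| 98 | 0.886 | 0.936 |
| Averaged, 115 enrolled | 0.881 | 0.932 |
| Averaged, 118 enrolled | 0.900 | 0.944 |

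The chance of advancing a regimen with a true rate of 0.15 is one minus each entry. With 10 or fewer as the passing count it is 9.9% at 100, 11.4% at 98 and 11.9% averaged over 115 enrolled. With rejection at 10 or more it is 5.5%, 6.4% and 6.8%. The stated 89% power implies 11%.

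**7. Effect on type I error.** The shortfall does not raise it. At p = 0.05, P(X >= 11) is 0.0115 at 100 and 0.0099 at 98; P(X >= 10) is 0.028 at 100 and 0.025 at 98. All are below the stated 0.10.

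**The case against.** The strongest reply is that the slip has almost no consequence. Much of that stands. With 98 eligible and 10 or fewer as the passing count, power is 88.6%, which rounds to the stated 89%. Averaged over the number eligible it is 88.1%, about one percentage point below the stated figure. Under the other printed rule, power stays well above 89% and nothing is lost against what the protocol claims. None of this makes the three figures agree, so the arithmetic point remains.

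Three stronger readings are tempting, and the protocol does not support them.

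- **A reader might infer that the design fails without 100 eligible patients.** One hundred is the stated target, not a mathematical minimum. An exact single-stage rule with type I error at most 0.10 and power at least 0.89 already exists at 59 patients (reject at 6 or more: type I error 0.074, power 0.894).
- **A reader might infer that the shortfall breaches a 10% limit on advancing a regimen that is too toxic, so that a lower cut-off is needed below 100 patients.** The protocol sets no such limit. Its stated power accepts 11%. A new boundary would also rest on an unresolved contradiction about exactly 10 events.
- **A reader might infer that enrolling 118 secures 100 eligible patients.** It does so only in expectation; the chance of falling short is still 41%.

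**Conclusion.** The enrolment figure is wrong as stated. At 15% ineligibility, 115 enrolled gives 97.75 expected eligible; it matches a rate of 13.0%, and 15% needs 118. The consequence is minor. Against 100 eligible patients, averaged power falls by about 2 points (0.901 to 0.881) if 10 or fewer is the passing count, or just over 1 point (0.945 to 0.932) if 10 or more rejects. Against the stated 89%, the loss is about 1 point under the first rule and none under the second.

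This rests on four assumptions: the 15% is a fraction of those enrolled; patients are ineligible independently of one another; the test is run on eligible patients only, which is what an ineligibility allowance implies; and every eligible patient is evaluable at 2 years. Loss or death before 2 years would lower the denominator further, but the protocol gives no rate for it and none is assumed here.

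**What to change.** Correct the sentence in Protocol section 8, Study Design, in one of two ways:

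- state 118 enrolled for 100 expected eligible at 15% ineligibility; or
- keep 115 and state that it allows for 13% ineligibility, with about 98 eligible expected if the rate is 15%.

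Then restate the power for the expected eligible number. That has to wait until the two statements about exactly 10 events have been reconciled, because the power depends on which one holds. No change of cut-off is needed on account of this point.

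The cost is a corrected sentence and a recalculated power figure. The first option adds 3 patients to planned enrolment; the second adds none.
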